Experimental Procedure (visit 2/day 7 (+/- 1day)): This visit will take approximately 5-7 hours. Subjects will arrive and complete the CFQ-R CF Questionnaire. FENO will be measured as above. If the subject had no serious adverse events for the first seven days of the 45 mg dose of nebulized sodium nitrite, and has stable systemic blood pressure and FEV₁ on presentation to the Day 7 visit, an electronic nebulizer will be used to deliver 90 mg of nebulized sodium nitrite. Subjects will be monitored closely for the next two hours, including percutaneous measurements of oxygen saturation and methemoglobin levels, recorded at minutes 15, 30, 60 and 120, and noninvasive systemic blood pressure measurements every 15 minutes. If percutaneous methemoglobin measurements exceed 5%, they will be confirmed by venous blood measurement. Spirometry will be repeated at 30 and 120 minutes following nebulized sodium nitrite administration. If nebulized sodium nitrite is tolerated, then the subject will be dispensed an 8 day supply of 90 mg nebulized sodium nitrite dosed two times daily and discharged from the CTRC, CHP or the Emphysema Research Center in Montefiore. If the 90 mg dose of nebulized sodium nitrite was not tolerated, the subject will be observed. If FEV₁ returns to baseline in 4 hours and subject's SaO₂ is not greater than 5% drop from baseline and systolic BP is not greater than 40 mm Hg drop from pre-dose baseline, the subject will be re-challenged at this visit with a 45 mg dose of nebulized sodium nitrite and the observation protocol of blood pressure measurements, spirometry and percutaneous oxygen saturation measurement will be repeated.

Experimental Procedures (visit 3/day 14(+/- 1day)): This is a safety and tolerability visit and will take approximately 1 hour. Subjects will complete the CFQ-R and spirometry. An oral wash will be collected, and then a sputum sample will be collected. If the subject cannot spontaneously expectorate, then sputum induction will be done. The subject will then be discharged with a 15 day supply of nebulized sodium nitrite.

Experimental Procedures (visit 4/day 28(+/- 1day)): This visit will take approximately 1.5 hours. Subjects will complete the CFQ-R and spirometry. Expectorated or induced sputum will be collected, an oral wash will be collected, and FE_{NO} measured as above. Sputum will be used to measure nitrite concentration and quantitative bacterial load.

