If subjects spontaneously expectorate, then sputum induction will not be done. After sputum induction, subjects will wait a minimum of 30 minutes prior to nebulization of nebulized sodium nitrite because sputum induction can cause temporary bronchoconstriction and this might confound the safety assessment of nebulized sodium nitrite. The amount of wait time will be determined by the physician investigator at the time of visit. Sputum induction will be done on Study days 0, 14, 28, and 42. If no further administration of nebulized sodium nitrite is planned during the visit (Days 14, 28, and 42), subjects may leave after sputum induction if they are not symptomatic.

Nebulization of Drug: nebulized sodium nitrite will be nebulized via electronic nebulizer with direct observation by a study physician or nurse coordinator on day 0, and at dose escalation by a study physician or nurse coordinator on day 7 in the CTRC, CHP or an Emphysema Research Center room in Montefiore. Subsequent doses will be self-administered by the subjects two times daily at home.

CFQ-R Questionnaire: Subjects will complete this standard and validated questionnaire on paper. Results of the CFQ-R will be confidentially stored electronically. Original paper will be maintained and stored in the locked Pulmonary Medicine Allergy and Immunology office.

NIOX device: Subjects exhale slowly through the device as guided by a small video screen with a smiling cloud icon. Disposable filters are used for each subject to minimize infection control concerns with the device. NIOX data will be recorded on days 0, 7 and 28.

Phlebotomy: Blood will be drawn by trained personnel at the screening visit (and day 0 if labs require repeating). Peripheral blood for confirmatory methemoglobin level will be obtained if percutaneous methemoglobin levels exceed 5%.

Vital sign measurements: Pulse, systemic blood pressure, temperature, respiratory rate and pulse oximetry will be measured noninvasively by trained study personnel using standard clinical equipment. All these values will be measured on screening visit and days 0, 7 and 42 (exit exam). On days 0 and 7 when nebulized sodium nitrite is being administered with observation, percutaneous measurements of oxygen saturation and methemoglobin levels will be measured for two hours after delivery. Noninvasive systemic blood pressure measurements will be taken every 15 minutes for the first two hours.

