Subjects will be monitored carefully for adverse events, laboratory test abnormalities, and changes in vital signs. Adverse experiences will be evaluated according to criteria outlined in the NCI Common Terminology Criteria for Adverse Events (CTCAE), version 4.0

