2.11 SCHEDULE OF ACTIVITIES

Study Phase	Screening	Treatment				Follow-Up Monitoring
Visit Type	Outpatient	Outpatient				
Study Day	day -28 to -2	(visit 1) day 0 - +/- 1 day	(visit 2) day 7 - +/- 1 day	(visit 3) day 14 - +/- 1 day	(visit 4) day 28 - +/- 1 day	(visit 5) day 42 - +/- 5 day
Informed Consent	X					
Medical History and Demographics	X					
I/E Criteria	X					
Tolerability Determination for Dose Escalation			X			
Physical Exam	X	X				X
Vital Signs (Pulse, systemic blood pressure, temperature, respiratory rate and pulse oximetry)	X	X	X			X
Non-invasive blood pressure measurement		X	X			
Oxygen Saturation		X	X			
Laboratory Tests***	X					
Urine Pregnancy Test Δ	X					
Spirometry	X	X	X	X	X	X
Sputum Collection		X		X	X	X
FeNO		X	X		X	
oral wash		X		X	X	X
Percutaneous metHgb Level§		X	X		X	
CFQ-R symptom assessment		X	X	X	X	X
AE Assessment		X	X	X	X	X
Interval History Assessment						X

Δ Urine pregnancy test will be performed only on female of childbearing potential. *** Clinical laboratory tests may be repeated on study visit 1 if screen lab results deemed clinically significant and warrant repeat testing or inadvertently not collected at screen visit § Methemoglobin

(metHgb) levels: will be measured and recorded at the following time points: pre-dose, approx. 5, 15, 30, 60, and 120 minutes post each dose of nebulized sodium nitrite. If percutaneous measurements exceed 5%, then a venous blood sample will be drawn for confirmation. Peripheral blood for confirmatory methemoglobin level will be obtained 60 minutes after nebulization on study days 0 and 7 and for a final methemoglobin level on day 28.

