2.12.7 *Laboratory Testing* Peripheral blood samples will be evaluated for evaluation of study eligibility and includes complete blood count with differential, platelets, electrolytes, glucose, BUN, serum creatinine, and liver function tests (total bilirubin, ALT, AST, alkaline phosphatase). Urine pregnancy test may be performed only on female of child-bearing potential at screening. Screening lab samples may be collected and analyzed at UPMC laboratories or at outlying facility of subject's choice. Lab results will be added to research chart for comparison. Except for urine pregnancy tests, baseline laboratory results within 6 months of screen visit may be used as baseline comparison and will not be repeated for research purposes. Blood samples

may be collected on study visit 1 if baseline screening results are deemed clinically significant and warrant repeat testing or inadvertently not collected at screen visit.

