2.13 ENDPOINTS

2.13.1 Primary endpoint: The primary endpoint is FEV₁ to assess for bronchoconstriction induced by the study compound. We will compare FEV₁ before and at 30, and 120 minutes after dosing on day 0 with 45 mg dose, and day 7 with 90 mg dose. A sustained decrease in FEV₁ > 15% with the 45 mg dose will be considered intolerance and the study subject will be removed from the protocol. If a subject tolerates one week of the 45 mg dose but has a sustained decrease in FEV₁ after getting the first 90 mg dose, the subject will remain on the 45 mg dose for the duration of the study. If a subject experiences a CF respiratory exacerbation as defined by a drop in FEV₁ >15% on the first set of spirometry at any visit compared with baseline spirometry, then the subject will be removed from the study.

2.13.2 Secondary endpoints:

- FE_{NO} (exhaled NO)
- sputum nitrite concentrations
- CF Questionnaire-R subsection
- quantitative bacterial cultures for *P. aeruginosa* and/or *S. aureus*
- methemoglobin levels measured both non invasively and in whole blood
- systolic blood pressure

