5.2 PROTECTIONS AGAINST RISK

5.2.1 Protection Against Patient Risks Related to the Study Drug

The study has been designed with a focus on protecting subjects against risk from the medication including:

- Specific exclusion criteria to provide a stable population of subjects and non-enrollment of subjects with significant co-morbidities that might place them at excess risk (see exclusion criteria above).
- Continuous monitoring by the DSMB.
- Involvement by trained staff / investigators with experience in the administration of inhaled study medications.
- Specific holding criteria related to study adverse events.
- Frequent monitoring of vital signs and spirometry over the duration of the study.

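### No blood pressure or pulse reading is scheduled between the Day 7 visit and Day 42, so systolic BP, a secondary endpoint, has no planned measurement under repeated 90 mg dosing

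*Combined protocol and SAP*

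**What the plan says.** Section 2.10 (Vital sign measurements) names the days for pulse, blood pressure, temperature, respiratory rate and oximetry: "All these values will be measured on screening visit and days 0, 7 and 42 (exit exam". On Days 0 and 7 it adds BP every 15 minutes for two hours after the observed dose.

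In Section 2.11 the row "Vital Signs (Pulse, systemic blood pressure, temperature, respiratory rate and pulse oximetry" is marked at screening and Days 0, 7 and 42, and is blank at Days 14 and 28. The separate rows for non-invasive BP and oxygen saturation are marked at Days 0 and 7 only.

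The visit descriptions in Section 2.2.1 match. Of Day 14 the protocol says "This is a safety and tolerability visit and will take approximately 1 hour"; the content is CFQ-R, spirometry, oral wash and sputum. Day 28 has CFQ-R and spirometry, and then "Expectorated or induced sputum will be collected, an oral wash will be collected, and FE_{NO} measured as above". Neither lists vital signs. The Day 42 description does.

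Other sections promise more. Section 2.13.2 includes "systolic blood pressure" among the secondary endpoints, with no time points. Section 5.2.1 lists as a protection "Frequent monitoring of vital signs and spirometry over the duration of the study". Section 2.10 also states: "Subjects will be monitored carefully for adverse events, laboratory test abnormalities, and changes in vital signs". Section 2.5 explains that the interval visits, Days 14 and 28 among them, are there for subject safety.

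**The concern.** Section 2.5 names hypotension, with methemoglobinemia, as a risk known from earlier studies, and relies on careful monitoring to manage it. Section 5.1.1 calls a fall in blood pressure, seen at 176 mg, the most important safety finding of the first-in-man study. Yet once a subject goes home on 90 mg, no BP or pulse is scheduled until treatment has been over for about two weeks.

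Two things are at stake. First, a named secondary endpoint cannot be reported for repeated dosing at the target dose, which is how the drug is taken for most of the trial. Second, adverse-event questioning does not fully replace measurement. Section 1.3.3 reports that one subject in the earlier patient studies was withdrawn for hypotension without symptoms, and Section 5.1.1 reports asymptomatic rises in heart rate at every dose. Findings of that kind appear only if someone takes a reading.

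**Working it through.** The plan states no figure for this gap, and its sample-size calculation does not involve blood pressure. The check is a comparison of sections followed by day counts.

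**Inputs**
- Visits at Days 0, 7, 14 and 28 (each ±1 day) and Day 42 (±5 days): Section 2.11.
- 45 mg for the first week, then 90 mg for the remaining three weeks: Section 2.2.1.
- Twice-daily self-administration at home after the observed doses: Section 2.10.
- Follow-up 14 ± 5 days after treatment ends: Section 2.4.

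**Do the operational sections agree?** Yes. The Section 2.10 text, the Section 2.11 rows and the visit descriptions in Section 2.2.1 all leave Days 14 and 28 without vital signs. The blank cells are therefore not a table-reading artefact.

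**Gap between scheduled BP readings after the Day 7 visit**
- Nominal: 42 − 7 = 35 days.
- Shortest: (42 − 5) − (7 + 1) = 29 days.
- Longest: (42 + 5) − (7 − 1) = 41 days.

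**Exposure at 90 mg, for a subject who escalates and stays at that dose**
- Nominal: 28 − 7 = 21 days, and 21 × 2 = 42 doses. One is observed on Day 7, leaving 42 − 1 = 41.
- Shortest: (28 − 1) − (7 + 1) = 19 days, or 38 doses, of which 37 are unobserved.
- Longest: (28 + 1) − (7 − 1) = 23 days, or 46 doses, of which 45 are unobserved.

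**Time off drug at the next reading:** 42 − 28 = 14 days nominal, or 9 to 19 days under Section 2.4.

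**Scheduled on-treatment BP readings after the Day 7 visit:** 0 as written. With readings added at Days 14 and 28 there would be 2. The intervals would be 14 − 7 = 7, 28 − 14 = 14 and 42 − 28 = 14 days, so the longest falls from 35 to 14 days. No sample-size or power figure changes.

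**The case against.** The best defence is that BP monitoring is placed where the effect is expected. Section 1.3.3 says the hypotension at 176 mg came immediately after nebulization, and Section 1.3.1 gives an intravenous half-life of 51 minutes, possibly longer when inhaled. Readings every 15 minutes for two hours after the first dose at each level suit that profile. No dose is planned in clinic at Days 14 or 28, so a reading there would come at an uncontrolled time after a home dose and could miss the low point. Section 2.13.2 sets no time points, so the Day 0 and Day 7 series could serve the endpoint. Section 1.3.3 also reports no other dose-limiting toxicity at 90 mg, and good tolerance of 46 or 80 mg four times daily for up to 16 weeks in pulmonary hypertension. The operational sections agree with one another, so the mismatch with Section 5.2.1 could be settled by rewording.

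Much of this stands. The acute response is well covered, and a Day 14 or 28 reading is an imperfect measure. But the prior experience cited for repeated dosing is in healthy volunteers and in pulmonary hypertension or heart failure, whereas this trial's objective is safety in adults with CF. Rewording would remove the contradiction but leave the endpoint without repeated-dose data at 90 mg.

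A reader might go further and infer any of the following. The documents do not support them.
- *Only the two first doses inform blood pressure.* Section 2.2.1 requires stable systolic BP on arrival at Day 7, before escalation. That reading follows a week of twice-daily 45 mg.
- *The whole safety conclusion rests on single-dose data.* FEV₁, the primary endpoint, is scheduled at Days 14 and 28, as are CFQ-R and adverse events, and percutaneous methemoglobin is scheduled at Day 28.
- *Vital signs and saturation are never taken at those visits.* Section 2.10 includes an initial vital-signs check in sputum induction, and Section 2.12.4 describes a co-oximeter that also reads saturation, so a Day 28 value may exist. But induction covers only subjects who cannot expectorate and does not name BP. Neither source supplies the endpoint.

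**Conclusion.** The point holds for scheduled blood pressure and pulse under repeated 90 mg dosing. There are no planned on-treatment readings after the Day 7 visit. Nominally 41 of 42 doses at 90 mg follow the last one, the gap is 35 days (29 to 41), and the next reading is about 14 days (9 to 19) after treatment ends. Section 5.2.1 and the stated purpose of the Day 14 and 28 visits do not fit that schedule. This is worth correcting because the remedy is cheap. It does not undermine the primary endpoint or the acute BP data.

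The counts assume full twice-daily adherence, escalation on Day 7 and treatment ending at Day 28, as Sections 2.2.1 and 2.4 imply. The synopsis gives a treatment duration of 56 days, which does not match those sections; the counts follow the body text. Subjects kept at 45 mg have the same measurement gap but not the same dose.

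The statement in Section 2.10 on laboratory abnormalities might suggest that this point extends to missing on-treatment laboratory panels. It does not. Section 2.12.7 presents the panel as an eligibility assessment, and on older results says: "Except for urine pregnancy tests, baseline laboratory results within 6 months of screen visit may be used as baseline comparison". Whether a venous sample is drawn at Day 28 is itself unsettled: the Section 2.11 footnote calls for one, while the Phlebotomy paragraph of Section 2.10 provides for a post-screening methemoglobin draw only when the percutaneous level exceeds 5%. That conflict needs reconciling separately.

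**What to change.** Reconcile Sections 2.10 and 2.11 with Section 5.2.1 by adding BP, pulse and SpO2 to the existing Day 14 and Day 28 visits, in the procedures text, the schedule and the visit descriptions. Record the time since the last home dose and the current dose level with each reading.

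In Section 2.13.2, give the systolic BP endpoint time points: the acute Day 0 and Day 7 series, and separately the Day 14 and Day 28 values as a descriptive repeated-dose result. Report time since dose beside the latter, so that they are not read as post-dose minima.

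The cost is a few minutes of non-invasive measurement at each of two visits already held, with no new visit and no change in sample size. The limitation is that readings at uncontrolled times after a home dose may miss the post-dose low.

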2.11 SCHEDULE OF ACTIVITIES

Study Phase	Screening	Treatment				Follow-Up Monitoring
Visit Type	Outpatient	Outpatient				
Study Day	day -28 to -2	(visit 1) day 0 - +/- 1 day	(visit 2) day 7 - +/- 1 day	(visit 3) day 14 - +/- 1 day	(visit 4) day 28 - +/- 1 day	(visit 5) day 42 - +/- 5 day
Informed Consent	X					
Medical History and Demographics	X					
I/E Criteria	X					
Tolerability Determination for Dose Escalation			X			
Physical Exam	X	X				X
Vital Signs (Pulse, systemic blood pressure, temperature, respiratory rate and pulse oximetry)	X	X	X			X
Non-invasive blood pressure measurement		X	X			
Oxygen Saturation		X	X			
Laboratory Tests***	X					
Urine Pregnancy Test Δ	X					
Spirometry	X	X	X	X	X	X
Sputum Collection		X		X	X	X
FeNO		X	X		X	
oral wash		X		X	X	X
Percutaneous metHgb Level§		X	X		X	
CFQ-R symptom assessment		X	X	X	X	X
AE Assessment		X	X	X	X	X
Interval History Assessment						X

Δ Urine pregnancy test will be performed only on female of childbearing potential. *** Clinical laboratory tests may be repeated on study visit 1 if screen lab results deemed clinically significant and warrant repeat testing or inadvertently not collected at screen visit § Methemoglobin

(metHgb) levels: will be measured and recorded at the following time points: pre-dose, approx. 5, 15, 30, 60, and 120 minutes post each dose of nebulized sodium nitrite. If percutaneous measurements exceed 5%, then a venous blood sample will be drawn for confirmation. Peripheral blood for confirmatory methemoglobin level will be obtained 60 minutes after nebulization on study days 0 and 7 and for a final methemoglobin level on day 28.

2.12 DESCRIPTION OF STUDY PROCEDURES

2.12.1 *Sputum Induction*

Please see description in 2.10 above and in the SOP in the appendix.

2.12.2 *Spirometry*

Spirometry will be used to measure FEV₁. All CF subjects undergo spirometry at every outpatient visit, and have extensive experience with the procedure. A handheld spirometer will be used.

2.12.3 *Oral Washes*

Subjects will be asked to brush teeth with a clean, single use toothbrush. Next subjects will be given 10 ml of 0.9% salt water solution and instructed to swish and gargle for 1 full minute before spitting the salt water solution into a sterile specimen cup.

2.12.4 *Percutaneous Oxygen Saturation and Methemoglobin:* The device (Masimo Rainbow SET® CO-Oximeter) selected for use in this clinical trial has been validated to provide accurate determinations of both SaO₂ and methemoglobin levels under conditions of hypoxia and methemoglobinemia. SaO₂ and methemoglobin monitoring will occur prior to study drug administration until 2 hours post-dose. Measurements will be recorded pre-dose, approx. 5, 15, 30,60, and 120 minutes post each dose of nebulized sodium nitrite.

2.12.5 *CFQ-R Questionnaire*

Subject symptoms will be measured using the Cystic Fibrosis Questionnaire – Revised (CFQ-R), which is the best validated and most widely used disease specific instrument for measuring health-related quality of life in CF(20). The CFQ-R was used during evaluation of inhaled amikacin, inhaled aztreonam, and ivacaftor. The Minimal Clinically Important Difference for CFQ-R is 4.0 for stable patients and 8.5 during an exacerbation, thus a threshold of 4.0 point change will be used to define a meaningful change(21).

2.12.6 *Exhaled NO measurements*

FE_{NO} measurement will be done with a NIOX MINO device. This is a noninvasive test that involves the subject slowly exhaling through the measurement device for a 10-second period of time. The device is in widespread clinical use for the assessment of asthma severity.

2.12.7 *Laboratory Testing* Peripheral blood samples will be evaluated for evaluation of study eligibility and includes complete blood count with differential, platelets, electrolytes, glucose, BUN, serum creatinine, and liver function tests (total bilirubin, ALT, AST, alkaline phosphatase). Urine pregnancy test may be performed only on female of child-bearing potential at screening. Screening lab samples may be collected and analyzed at UPMC laboratories or at outlying facility of subject's choice. Lab results will be added to research chart for comparison. Except for urine pregnancy tests, baseline laboratory results within 6 months of screen visit may be used as baseline comparison and will not be repeated for research purposes. Blood samples

may be collected on study visit 1 if baseline screening results are deemed clinically significant and warrant repeat testing or inadvertently not collected at screen visit.

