Exclusion Criteria:	
1. Inability to provide consent2. Use of supplemental oxygen or non-invasive ventilatory support3. FEV₁ < 40%4. Awaiting lung transplantation5. Pregnancy or unwilling to comply with birth control during the intervention period6. History of glucose-6-phosphate dehydrogenase (G6PD) deficiency or any contraindication to receiving methylene blue7. Hospitalization within the past 4 weeks prior to enrollment8. Subject requires additional antibiotics or steroids within the past 4 weeks prior to enrollment9. Change in maintenance CF therapies in the past 4 weeks prior to enrollment10. Baseline systemic hypotension (systolic BP < 90 mm Hg)11. History of orthostatic hypotension or syncope12. Chronic kidney disease (creatinine > 2.5 or requiring dialysis)13. Severe anemia (Hgb <9 gm/dL in the last six months)14. History of portal hypertension or chronic liver disease, including hepatitis B and/or hepatitis C (with evidence of recent infection and/or active virus replication), defined as moderate to severe hepatic impairment (Child-Pugh Class B-C)15. History of abusing alcohol or illicit drugs within 28 days prior to study16. Severe pulmonary hypertension (mean PA pressure > 25)17. Use of sildenafil or other pulmonary vasodilator18. History of any organ transplantation19. Participation in another interventional trial in the previous 28 days
Study Endpoints:	
Primary endpoint:
 
The primary safety and efficacy endpoint is FEV₁. A sustained decrease in FEV₁ of >15% will be considered intolerable.
 
Secondary endpoints include exhaled NO (FE_{NO}), sputum nitrite concentration, quantitative bacterial cultures, percutaneous methemoglobin levels, blood pressure, and subject symptoms as measured by the CF Questionnaire-R.

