Experimental Procedures (visit 1/day 0 (+/- 1day)): This visit will take approximately 5 hours. Subjects will arrive and complete the CFQ-R CF Questionnaire. Vital signs will be recorded and a physical examination performed, subjects will provide a sputum sample if able, and complete an oral wash specimen. The fractional excretion of nitric oxide (FENO) will be measured using a NIOX device, and baseline spirometry will be obtained. If subjects are unable to spontaneously expectorate sputum, then sputum induction will be done, followed by at least a 30 minute observation period because sputum induction is associated with temporary bronchoconstriction which might confound further measurements. The observation period will be omitted in subjects that spontaneously expectorated sputum. Next, an electronic nebulizer will be used to deliver 45 mg of nebulized sodium nitrite. Subjects will be monitored closely for the next two hours, including percutaneous measurements of oxygen saturation and methemoglobin levels, recorded at minutes 15, 30, 60 and 120, and noninvasive systemic blood pressure measurements every 15 minutes. Spirometry will be repeated at 30 and 120 minutes following nebulized sodium nitrite administration. If percutaneous methemoglobin measurements exceed 5%, they will be confirmed by venous blood measurement. If nebulized sodium nitrite is tolerated, then the subject will be dispensed an 8 day supply of 45 mg nebulized sodium nitrite dosed two times daily and discharged from the CTRC, CHP or the Emphysema Research Center in Montefiore. If the 45mg dose of nebulized sodium nitrite is not tolerated, the subject will be observed until stable and then discharged from the CTRC, CHP or the Emphysema Research Center in Montefiore.

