3.1.1 Inclusion of Women and Minority

Both men and women of all races and ethnic groups are eligible for this trial. Women who meet the inclusion criteria, and have none of the exclusion criteria, will be enrolled without restriction as dictated by the study protocols. Because of the use of a study medication, woman of child bearing potential must meet specialized inclusion/exclusion criteria to minimize this risk.

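### The only scheduled pregnancy test is at screening, so the result is nominally 2 to 28 days old at the first 45 mg dose; a repeat at Visit 1 would be a cheap, minor safeguard

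*Combined protocol and SAP*

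**What the plan says.** **The exclusion and its reason.** Item 5 of the synopsis exclusion list reads "Pregnancy or unwilling to comply with birth control during the intervention period", and section 3.3 repeats it. Section 5.1.5 says that the drug's effect on an unborn child is unknown. Section 3.1.1 adds that, because a study medication is used, "woman of child bearing potential must meet specialized inclusion/exclusion criteria to minimize this risk".

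**The test.** Section 2.12.7 says: "Urine pregnancy test may be performed only on female of child-bearing potential at screening". The footnote to the schedule in 2.11 says: "Urine pregnancy test will be performed only on female of childbearing potential". That row has one mark, under screening (day -28 to -2). Sections 2.2.1 and 2.10 also list the test among the screening evaluations. Section 2.12.7 exempts pregnancy tests from the rule that lets laboratory results from the previous six months be reused.

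**Visit 1.** Section 2.2.1 lists the questionnaire, vital signs, physical examination, sputum, oral wash, exhaled nitric oxide and spirometry, then the dose: "Next, an electronic nebulizer will be used to deliver 45 mg of nebulized sodium nitrite". No pregnancy test appears. In 2.11 the row for inclusion and exclusion criteria is marked at screening only, and the row "Interval History Assessment" at Visit 5 only.

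**The conditional repeat.** The schedule allows that "Clinical laboratory tests may be repeated on study visit 1 if screen lab results deemed clinically significant and warrant repeat testing", or if the sample was missed at screening. This footnote belongs to the laboratory tests row. The matching sentence in 2.12.7 is about blood samples, which "may be collected on study visit 1 if baseline screening results are deemed clinically significant and warrant repeat testing".

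**The concern.** The exclusion exists to prevent fetal exposure to a drug of unknown reproductive risk. The first dose is the last point at which that exposure can be prevented entirely. The plan verifies the exclusion by test once, before that point, and the interval can run to four weeks.

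Long intervals can follow from the plan's own scheduling. For subjects on inhaled antibiotics, 2.2.1 sets Visit 1 at 2 to 7 days after the next scheduled inhaled antibiotic starts, and 1.3.1 describes these drugs as cycled monthly.

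The authors already treat pregnancy results as perishable, since they exempt them from the six-month reuse rule. The same reasoning was not carried forward to the day of dosing. After that day no further test is scheduled, so a pregnancy missed at screening could be exposed to twice-daily dosing for up to 28 days unless the subject recognises and reports it. Section 5.4 expects no direct benefit to subjects, so there is nothing on the subject's side to offset the exposure.

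**Working it through.** The plan gives no figure for this point, so there is nothing to reproduce. The check has three parts: the age of the result at first dose, the possible routes to a Visit 1 test, and a bound on how many cases that test could catch.

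**1. Age of the result at the first dose.** Inputs: screening window day -28 to -2 and Visit 1 on day 0, plus or minus 1 day (2.11).

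- Nominal: 0 - (-2) = 2 days at least; 0 - (-28) = 28 days at most.
- With the Visit 1 window, counting screening days from nominal day 0: 2 - 1 = 1 day to 28 + 1 = 29 days.
- With a test before dosing at Visit 1: 0 days.

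The documents give no distribution of the interval inside the window, so no typical value is used.

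**2. Could a Visit 1 test arise by another route?**

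| Provision | Where | Covers the pregnancy test at Visit 1? |
|---|---|---|
| Pregnancy test row | 2.11 | No, screening only |
| Entry criteria row | 2.11 | No, screening only |
| Visit 1 procedures before dosing | 2.2.1 | No |
| Conditional laboratory repeat | 2.11, 2.12.7 | No, clinical laboratory tests and blood samples |
| Removal if FEV₁ before dosing has fallen more than 15% from screening | 2.6 | No, lung function only |

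**3. How many cases could a Visit 1 test catch?** Let W be the number of women of childbearing potential, p the conception rate per 28 days and g the interval in days. Then

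expected catches = W × p × g/28.

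*Rate needed for one expected catch.* W cannot exceed the planned 35, and g = 28 is the nominal maximum.

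- W = 35, g = 28: p = 1/35 = 2.9% per 28 days; yearly 1 - (1 - 0.0286)^(365.25/28) = 0.31.
- W = 18 (about half the sample, an assumption), g = 28: p = 1/18 = 5.6% per 28 days; yearly 1 - (1 - 0.0556)^(365.25/28) = 0.53.

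*Expected catches at assumed rates.* The documents give no conception rate, so I assume a range of 1% to 10% a year. Then p = 1 - (1 - yearly rate)^(28/365.25), which is 0.00077 at 1% and 0.0080 at 10%.

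| W | g | At 1% a year | At 10% a year |
|---|---|---|---|
| 35 | 28 | 0.03 | 0.28 |
| 35 | 2 | 0.002 | 0.02 |
| 18 | 28 | 0.01 | 0.14 |
| 18 | 2 | 0.001 | 0.01 |

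A urine test cannot see the earliest conceptions. If the detection delay is the same at both tests, the period that the second test adds is still g days long, but it starts and ends earlier by that delay. The formula therefore still holds. Part of the added period may fall before screening, when the study's contraception requirement does not yet apply.

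**The case against.** The strongest reply is that this is a consistent design choice with other controls around it. The procedure text, laboratory section and schedule all agree on screening. The plan sets no maximum age for the test and promises none on day 0. Women unwilling to use birth control are excluded, section 5.1.5 requires effective contraception and prompt reporting of a pregnancy, and 2.14 lists pregnancy as a ground for withdrawal. An old result cannot stand in for the screening test. On the arithmetic above, the expected number of catches is well under one. All of this stands, and it sets the weight of the point. It does not supply a test on the day of dosing: contraception can fail, and self-report requires that the subject already knows.

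A second reply is that the fix then relies on contraception and self-report for 28 days of dosing, although they were thought insufficient for the interval before it. That is fair. The distinction is that a test before the first dose can prevent exposure altogether, whereas a later test can only shorten it.

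Two stronger readings are tempting, and the documents support neither:

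- **That the protocol breaks its own rule.** Section 3.1.1 speaks of specialized criteria but fixes no test date, and the screening test plus the contraception criterion can satisfy it.
- **That nothing about fitness for the study is checked again at Visit 1.** The physical examination, vital signs and spirometry are repeated before dosing, and section 2.6 removes a subject whose FEV₁ before dosing has dropped more than 15% from screening. What is missing is narrower: a pregnancy test and a formal entry-criteria mark.

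**Conclusion.** The point holds as a minor one. The sole scheduled pregnancy test is nominally 2 to 28 days old at first dose (1 to 29 with the visit window), and no scheduled step at Visit 1 tests for pregnancy.

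A reader might infer that a pregnant subject is likely to be dosed. The numbers do not bear that out. With every assumption pushed to its limit (35 women of childbearing potential, 28 days each), one expected catch needs conception at about 31% a year, which does not fit required effective contraception. At the assumed 1% to 10% a year, the same extreme gives 0.03 to 0.28 expected catches, and less for fewer women or shorter intervals.

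The case for changing the plan rests on the unknown and possibly irreversible nature of the harm and on the very low cost of the check. It does not rest on frequency. The FEV₁ endpoint, sample size and analysis are unaffected. The conclusion on size assumes that contraception is used broadly as required. The conclusion on timing assumes only the stated windows.

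**What to change.** For women of childbearing potential, require a negative urine pregnancy test at Visit 1 before the 45 mg dose. Three edits do this:

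- **2.2.1, Visit 1:** add the test to the procedures before nebulization and make a negative result a condition of dosing.
- **2.11:** add a mark under Visit 1 in the urine pregnancy test row.
- **2.12.7:** state that the test is done at screening and again at Visit 1 before dosing.

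The cost is one extra urine test per eligible woman, at an existing visit of about five hours, with no added visit or invasive procedure. Very early conceptions would still be missed, so the contraception, self-report and withdrawal provisions must stay.

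The synopsis gives the treatment duration as 56 days, while the body gives 28 (7 at 45 mg plus 21 at 90 mg). That is a separate editorial correction and adds no weight to this point.
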